## 1. Rationale

Prostate cancer (PCa) has become a major threat to male urogenital health. The global cancer statistics report published by the WHO's International Agency for Research on Cancer (IARC) showed 1.5 million new cases of prostate cancer worldwide in 2022, accounting for 7.3% of all malignant tumors and ranking second only to lung cancer in male morbidity. The incidence of prostate cancer shows significant geographical and ethnic differences. Historically, Asia has had a lower incidence rate compared to regions like Europe, America, Australia, and New Zealand. However, with an aging population, changes in lifestyle, and the popularization of screening methods such as prostate-specific antigen (PSA) testing, the incidence of prostate cancer in China is also showing a year-on-year upward trend. This growth has positioned China among the world leaders in both absolute numbers of new prostate cancer cases and deaths, signaling that prostate cancer has transformed from a relatively rare tumor into a major public health issue threatening the health of Chinese men [1].

Radical Prostatectomy (RP) is the standard method for treating localized prostate cancer, effectively removing tumor tissue and extending patient survival. However, this life-saving surgery also brings almost inevitable functional sequelae. Postoperative urinary incontinence, especially the immediate continence issue after catheter removal, severely impacts patients' quality of life. Studies show that some patients face immediate urine leakage or control difficulties after catheter removal, with an incidence rate between 5%-48% [2]. One study accurately quantified the amount of urine leakage using the 24-hour pad test, finding that in the first week after catheter removal, the average daily urine leakage could be as high as 408.0 mL [3]. This level is sufficient to cause severe social embarrassment and psychological distress, urgently requiring effective interventions.

Currently, the treatment for post-RP urinary incontinence mainly relies on conservative therapies such as Pelvic Floor Muscle Training (PFMT). However, these measures are usually initiated *after* catheter removal and cannot meet the need for immediate continence upon removal. Furthermore, the efficacy of PFMT requires long-term adherence, patient compliance is generally poor, and most importantly, **the timing of the intervention is delayed**. Traditional surgical interventions, such as the implantation of an artificial urinary sphincter (AUS) or male sling surgery, can improve symptoms but carry risks like infection and mechanical failure, and not all patients are suitable for such invasive treatments [2]. In terms of drug therapy, the several classes of drugs currently under investigation (including anticholinergics, PDE5 inhibitors, duloxetine, etc.) still lack evidence and remain controversial [4], and cannot be used as standard therapy for post-RP urinary incontinence patients. There is currently a lack of effective and widely recognized solutions for immediate continence intervention after catheter removal.

Against the backdrop of existing treatments failing to meet clinical needs, this study proposes early postoperative acupuncture as an innovative and scientifically rational intervention strategy. Acupuncture is not merely an "alternative therapy" but an effective **"non-invasive peripheral neuromodulation technique"** confirmed by modern medical research. Its theoretical basis for improving immediate postoperative continence is built on solid neurophysiological foundations and evidence from previous clinical studies. The core pathology of post-RP urinary incontinence is neuromuscular dysfunction. Acupuncture therapy, by stimulating specific acupoints on the body surface, can activate corresponding neural pathways, thereby modulating the function of the bladder and urinary sphincter. Its possible mechanisms of action include: **Direct sacral neuromodulation** (The deep anatomical location of the Baliao (BL31-BL34) acupoints corresponds precisely to the sacral foramina, and needle stimulation can directly act on the sacral nerve roots. This is mechanistically similar to Sacral Neuromodulation (SNS) therapy, which is already widely used clinically [5].) and **Activation of the pudendal nerve-sphincter pathway** (Stimulating sacral acupoints like Baliao can activate the afferent and efferent fibers of the pudendal nerve, enhancing the tension and closure function of the external urinary sphincter, thereby increasing urethral resistance and preventing involuntary urine leakage [6]).

Multiple studies have already shown that acupuncture has a certain effect in alleviating postoperative urinary incontinence. For example, in a study conducted by Yang Hao et al. [7], a clear conclusion was drawn by comparing the effects of "pudendal nerve electroacupuncture stimulation" versus "pelvic floor biofeedback electrical stimulation" in treating 81 patients with post-prostatectomy urinary incontinence. The study found that electroacupuncture therapy not only took effect faster (improvement at 4 weeks vs. 8 weeks for the control group) but also had a significantly higher total effective rate at 12 weeks (73.17% vs. 37.50%). Furthermore, the electroacupuncture group outperformed the control group on all quality of life and functional scores, and its efficacy remained stable during a follow-up period of up to 6 months, demonstrating good long-term effects. However, most existing research focuses on the treatment of long-term postoperative urinary incontinence, with **few studies** addressing the improvement of immediate continence after catheter removal.

Therefore, the core innovation of this study lies in the **"timing" of the acupuncture treatment**, specifically **early acupuncture therapy**. To be precise, we will perform acupuncture treatment during the postoperative window **before catheter removal** (while the bladder is in a "resting" state with continuous drainage via the catheter). The core hypothesis is: By applying neuromodulatory stimulation in advance, the urinary control system can be **"pre-activated" and "functionally reorganized" before** it faces the actual challenge (i.e., bladder filling and urination after removal). This may be achieved through the following pathways: **Re-establishing neural connections** (Activating and "awakening" neural pathways temporarily suppressed

by surgical trauma.), **Enhancing baseline sphincter tone** (Preemptively increasing the resting tension of the external urinary sphincter through pudendal nerve stimulation.), **Stabilizing detrusor function** (Inhibiting potential, uncoordinated detrusor contractions to prepare for stable bladder filling.), and **Reducing local inflammatory response** (Acupuncture has a recognized anti-inflammatory effect, which can help reduce surgical site edema and nerve irritation, creating a more favorable local microenvironment for functional recovery.) This "pre-emptive" intervention aims to adjust the patient's neuromuscular system to a better state of readiness, enabling it to more effectively cope with the pressure of bladder filling at the moment of catheter removal, thereby achieving a smoother transition in urinary control function and shortening or even avoiding a severe immediate incontinence period.

In summary, the early acupuncture intervention protocol proposed in this study not only possesses a solid neurophysiological basis and ample supporting evidence but also represents a shift in clinical thinking from "passive treatment" to "active prevention." By implementing non-invasive neuromodulation at a critical time window, it is expected to fill a huge gap in current clinical practice and provide a safe, effective, and economical new pathway for improving the immediate postoperative quality of life for prostate cancer patients. The specific objective is: To systematically evaluate the efficacy of early acupuncture treatment by comparing the **treatment group** (early acupuncture + standard care) versus the **control group** (no acupuncture + standard care) in terms of urine leakage volume, proportion of complete continence, pad usage, and patient satisfaction within 24 hours after catheter removal.

## Study Rationale and Significance

This study focuses on the impact of early postoperative acupuncture intervention on immediate urinary continence after catheter removal, filling a gap in existing research. Early postoperative intervention may accelerate the recovery of urinary control function by stimulating relevant nerves and muscles, reducing the risk of immediate urine leakage after removal. If the study yields positive results, early electroacupuncture treatment can provide patients with a non-invasive and safe treatment option, significantly improving postoperative quality of life and reducing the use of pads and the associated psychological burden.

Our team expects to conduct a prospective randomized controlled study (a collaboration between the Department of Urology at Zhongda Hospital, Southeast University; the Department of Urology at Nanjing Lishui People's Hospital; and the Department of Urology at Wuxi Xishan People's Hospital). Information on patients receiving treatment will be obtained from the electronic medical record (EMR) systems of Zhongda Hospital, Nanjing Lishui People's Hospital, and Wuxi Xishan People's Hospital. Patients meeting the inclusion and exclusion criteria will be screened and subsequently receive electroacupuncture treatment postoperatively. By following up with these patients and comparing them with postoperative patients receiving placebo electroacupuncture, we will study the impact on patient prognosis.

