## II. Study Content

### 1. Study Objectives

To evaluate the effect of early electroacupuncture intervention on immediate urinary continence after prostatectomy in a prospective study.

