### Outcome Measures

Follow-up on patient's urinary continence at 1 week, 4 weeks, 8 weeks, 12 weeks, and 24 weeks after catheter removal (half-year follow-up).

1. **Primary Endpoint:** Urine leakage volume (grams) measured by the first 1-hour pad test during the follow-up at 1 week post-catheter removal.
2. **1-hour Pad Test Results:** Conducted at the 4-week and 24-week follow-ups.
3. **ICIQ-SF Questionnaire Score:** At 1, 4, 8, 12, and 24 weeks post-removal to evaluate incontinence symptoms and their impact on quality of life. The proportion of completely continent patients (zero leakage) will directly quantify immediate continence.
4. **Self-Rating Anxiety Scale (SAS) Score:** To assess the potential improvement in patients' psychological state due to the acupuncture intervention.
5. **Voiding Diary and IPSS:** Patients will maintain a voiding diary and complete the International Prostate Symptom Score (IPSS) questionnaire at each follow-up node to assess nocturia and provide a comprehensive evaluation of urinary function.

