### Efficacy Evaluation

1. **Primary Endpoint:** Urine leakage volume (grams) measured by the first 1-hour pad test during the follow-up at 1 week post-catheter removal.
2. **1-hour Pad Test Results:** Conducted at the 4-week and 24-week follow-ups.
3. **ICIQ-SF Questionnaire Score:** At 1, 4, 8, 12, and 24 weeks post-removal to evaluate incontinence symptoms and their impact on quality of life. The proportion of completely continent patients (zero leakage) will directly quantify immediate continence.
4. **Self-Rating Anxiety Scale (SAS) Score:** To assess the potential improvement in patients' psychological state due to the acupuncture intervention.
5. **Voiding Diary and IPSS:** Patients will maintain a voiding diary and complete the International Prostate Symptom Score (IPSS) questionnaire at each follow-up node to assess nocturia and provide a comprehensive evaluation of urinary function.

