### Clinical Operational Feasibility

This study is designed as a multi-center, prospective, randomized controlled trial, planned to be conducted at Zhongda Hospital, Southeast University, and other medical institutions. Relying on the mature urological diagnosis and treatment platforms and prostate cancer patient databases at each center ensures the feasibility of patient recruitment. Participant information can be screened through electronic medical record systems. The inclusion criteria are clear and the exclusion criteria are strict, facilitating the rapid identification of the target population. The study expects to recruit 144 patients, 72 in each group; this sample size is calculated based on existing research data and is statistically reasonable.

The acupuncture intervention will be performed by qualified acupuncturists using standardized acupoints (e.g., Shenshu (BL23), Pangguangshu (BL28), Baliao (BL31-34), etc.). The procedure is simple and safe. The intervention is scheduled for one week post-prostatectomy, three times a week, 30 minutes per session. This is compatible with routine postoperative care and does not add burden to the patient. The assessment within 24 hours after catheter removal (e.g., pad test, proportion of complete continence) will be completed using standardized tools, making the outcome measurement objective and easy to implement. The follow-up plan (1 week post-removal and beyond) will be completed via telephone or outpatient visits, combined with the International Consultation on Incontinence Questionnaire-Short Form (ICIQ-SF), making data collection efficient and controllable.

Furthermore, each center is equipped with complete infrastructure, including sterile needles, treatment rooms, and data management systems, ensuring the smooth conduct of the trial. The research team consists of urologists, acupuncturists, and statisticians who have received standardized training, ensuring operational consistency and data quality. All participants will sign an informed consent form, and legal and ethical risks are manageable. In summary, this study is highly feasible at the clinical operational level and is capable of effectively advancing the trial process and obtaining reliable results.

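### The protocol calls electroacupuncture safe, as a premise and as something the study is expected to offer, but no listed outcome or analysis covers adverse events, so the trial as written cannot support the word.

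*Protocol*

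**What the plan says.** Three sections of the protocol describe the treatment as safe.

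- Study Rationale and Significance, on what follows if the results are positive: "early electroacupuncture treatment can provide patients with a non-invasive and safe treatment option".
- 1. Rationale, on what the approach is expected to do: "provide a safe, effective, and economical new pathway for improving the immediate postoperative quality of life".
- Clinical Operational Feasibility, as a plain assertion without data: "The procedure is simple and safe".

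The sections that define what is measured are confined to benefit. The objective reads: "To evaluate the effect of early electroacupuncture intervention on immediate urinary continence after prostatectomy in a prospective study". Outcome Measures lists five items, and Efficacy Evaluation repeats them. The first is "Urine leakage volume (grams) measured by the first 1-hour pad test during the follow-up at 1 week post-catheter removal". The others are later pad tests ("Conducted at the 4-week and 24-week follow-ups"), the ICIQ-SF with the proportion fully continent, the anxiety scale (SAS), and the voiding diary with IPSS. Section (4) Statistical Analysis deals with the primary and secondary endpoints, their missing data, and a subgroup analysis by type of incontinence. The supplied text nowhere provides for recording, grading or comparing adverse events.

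**The concern.** A statement that a treatment is safe needs data on harm, and the outcome list is where a protocol commits to collecting such data. Here the list is given twice and contains none. An analysis plan cannot repair this later, because it can only summarise what was collected.

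The gap matters more because exposure to harm is not the same in the two arms. Under (7) Treatment Methods the sham needles do not puncture the skin and carry no current, whereas the active arm receives 1-5 mA at lumbar and sacral points from postoperative day (POD) 7. That the active needles penetrate is implied by this contrast and by the mechanism described in 1. Rationale. A randomised comparison of harms is therefore available at little cost, and the plan does not take it. If the trial is positive on leakage, a report could repeat the word *safe* with nothing from the trial behind it.

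**Working it through.** **1. The plan's own figure.** The Sample Size paragraph gives a difference of 7.4 g, an SD of 14.9 g, two-sided alpha 0.05, power 0.80 and 1:1 allocation.

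n = (1.960 + 0.842)² × 2 × 14.9² / 7.4² = 63.64, so 64 per group.

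With 10% dropout: 64 / 0.90 = 71.11, so 72 per group and 144 in total (84 + 30 + 30 by site). The figure reproduces. It rests wholly on the pad test, and nothing in it is sized for safety.

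**2. The outcome list checked for harms.**

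| Listed item | What it measures | Captures adverse events? |
|---|---|---|
| 1-hour pad test, week 1 | leakage | no |
| 1-hour pad test, weeks 4 and 24 | leakage | no |
| ICIQ-SF, complete continence | incontinence symptoms | no |
| SAS | anxiety, framed as improvement | no |
| Voiding diary, IPSS | urinary function | no |

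None of the five items, in either list, is an adverse-event measure. ICIQ-SF and IPSS could show worse urinary symptoms, but not needle-site bleeding, infection, pain or nerve symptoms.

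**3. Timing.** Sessions are on POD 7, 9 and 11, and the catheter is removed on POD 14. The first listed outcome visit is one week after removal, about POD 21, which is 21 − 11 = 10 days after the last session. Clinical Operational Feasibility also mentions an assessment within 24 hours of removal, but only of continence, and says that follow-up may be by telephone. Brief needle-site events could be missed unless they are recorded as they happen.

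**4. What recording could show.** The protocol gives no adverse-event rate, so the rates below are assumptions shown as a range. The number treated is taken as 72 (all recruits in the active arm) or 64 (after the planned dropout).

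Upper bound when zero events are seen, one-sided 95%: 1 − 0.05^(1/n).

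- n = 72: 1 − 0.05^(1/72) = 0.0408, about 4.1%
- n = 64: 1 − 0.05^(1/64) = 0.0457, about 4.6%

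The upper limit of the two-sided exact 95% interval with n = 72 is 1 − 0.025^(1/72) = 0.0499, about 5.0%.

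Probability of seeing at least one event: 1 − (1 − p)^n.

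| Assumed true rate p | n = 72 | n = 64 |
|---|---|---|
| 1% | 0.515 | 0.474 |
| 2% | 0.767 | 0.726 |
| 5% | 0.975 | 0.962 |

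These figures describe what the trial could say if harms were recorded. As the plan stands, no such bound can be computed.

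**The case against.** The strongest reply is that *safe* is rationale language and not a result the trial undertakes to show. The sentence in Study Rationale and Significance says what the treatment can provide, 1. Rationale speaks of an expectation, and the feasibility section uses safety as a premise. The sections that state what the trial will deliver, 6. Innovative Aspects of the Project and Expected Research Outcomes, promise a new non-invasive intervention and do not use the word. This stands. A reader might infer that the plan turns a positive efficacy result into a finding of safety, but the documents contain no such rule and no safety hypothesis.

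A reader might also infer that the outcome lists are exhaustive and that harms will not be recorded at all. The documents do not support this either. Neither list is declared complete: both omit pad usage and patient satisfaction, which other sections name as comparisons. One list is headed as efficacy, so the absence of harms there is unsurprising. The text is silent on recording and does not exclude it; sites may note harms in routine care.

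Finally, how adverse events are tabulated is commonly left to an analysis plan, which is not shown. That answers a complaint about tables. It does not answer the collection gap, because by-arm harms that were not gathered systematically cannot be compared afterwards. Nor does it answer the positive use of the word in three sections.

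**Conclusion.** The point holds in a limited form. Three sections call the treatment safe, and no listed outcome or planned analysis covers adverse events, so the trial as written cannot support the word. The arms differ in exposure to current and, by implication, to skin penetration, so harms could differ between them unseen.

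The consequence is confined to what may be said about safety. The primary endpoint, its test, the sample size of 144 and any efficacy conclusion are untouched. Even with recording in place, 72 treated patients without an event would leave true rates up to about 4% unexcluded, so any safety statement would have to be cautious. That bound assumes that all 72 are treated and observed; the detection probabilities also rest on assumed event rates.

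**What to change.** - **Outcome Measures:** add adverse events by arm as a secondary (safety) outcome.
- **Efficacy Evaluation:** place a matching safety item beside the efficacy list.
- **Collection:** record events at each treatment session and at the existing follow-up contacts. Recording at sessions matters because later contacts may be by telephone, when needle sites cannot be inspected.
- **(4) Statistical Analysis:** summarise adverse events as counts with exact 95% confidence intervals, by treatment received.
- **Wording:** in 1. Rationale, Study Rationale and Significance, and Clinical Operational Feasibility, limit any safety statement to what these data show, or delete the word *safe*. If no adverse-event outcome is added, deletion is the only consistent choice.

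The cost is a short form at each session and contact, and a more modest safety statement. Sample size and efficacy analysis do not change.

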## II. Study Content

### 1. Study Objectives

To evaluate the effect of early electroacupuncture intervention on immediate urinary continence after prostatectomy in a prospective study.

### 2. Study Content

**(1) Selection of Study Sites:** This study will be conducted at the Department of Urology, Zhongda Hospital, Southeast University; the Department of Urology, Nanjing Lishui People's Hospital; and the Department of Urology, Wuxi Xishan People's Hospital.

**(2) Selection of Study Subjects:** Information on patients receiving acupuncture treatment and control group patients will be obtained from the multi-center EMR systems. Patients meeting the inclusion/exclusion criteria will be screened. Using block randomization, they will be allocated 1:1 into either the treatment group or the control group and receive either acupuncture treatment or sham acupuncture treatment for inclusion in the clinical study.

#### Number of subjects to be enrolled at each center:

- Department of Urology, Zhongda Hospital, Southeast University: 84 cases
- Department of Urology, Nanjing Lishui People's Hospital: 30 cases

- Department of Urology, Wuxi Xishan People's Hospital: 30 cases

**Sample Size:** This study is a prospective, multi-center, randomized, placebo-controlled clinical trial designed to assess the efficacy of early electroacupuncture intervention in improving immediate urinary continence after radical prostatectomy (RP). The Primary Endpoint has been determined as the urine leakage volume (in grams) measured by the 1-hour pad test administered immediately after catheter removal (within the first 1 hour post-removal). This calculation is based on a test comparing two independent sample means. The required parameters include the expected mean difference between groups (effect size,  $\delta$ ), the within-group standard deviation ( $\sigma$ ), the Type I error probability ( $\alpha$ ), and the Type II error probability ( $\beta$ ). We set the two-sided significance level  $\alpha = 0.05$ , statistical power  $(1-\beta) = 0.80$ , and a 1:1 allocation ratio for the two groups (treatment vs. sham acupuncture).

In the absence of a perfectly matched study focusing on post-RP males, comparing electroacupuncture versus sham acupuncture, and using the 1-hour pad test (grams) as the primary endpoint, we have, after rigorous screening, selected a high-quality, large-scale ( $N=504$ ), multi-center randomized controlled trial published by Liu et al. in the Journal of the American Medical Association (JAMA) in 2017 as the primary basis for parameter estimation. That study's methodological design (electroacupuncture vs. sham acupuncture) and primary outcome measure (1-hour pad test leakage volume) are highly consistent with our study, representing the best available evidence. Although its study population was women with stress urinary incontinence, we consider its reported effect size and variability data to be the most reasonable reference for this calculation, given the cross-gender commonality of the core physiological mechanism (sacral neuromodulation via electroacupuncture) for regulating urinary control.

Based on the results from Liu et al.'s study:

- **Expected Effect Size ( $\delta$ ):** The electroacupuncture group showed 7.4 grams more reduction in 1-hour pad test leakage compared to the sham acupuncture group. We use this as the expected mean difference between groups.
- **Within-group Standard Deviation ( $\sigma$ ):** Based on the reported 95% confidence interval of the effect size, we extrapolated the pooled standard deviation for the "change value" in leakage volume (before and after intervention) to be approximately 14.9 grams.

Based on the parameters above, using the sample size formula for comparing two independent means:  $n = [(Z\alpha/2 + Z\beta)^2 \times 2\sigma^2] / \delta^2$

The calculation shows that to achieve 80% power, **each group requires at least 64 subjects.**

Considering the short intervention cycle and clear follow-up nodes of this study, we estimate a dropout or withdrawal rate of approximately 10%. To compensate for this potential sample loss, the adjusted number of recruits needed per group is  $64 / (1 - 0.10) \approx 71.11$ . Rounding up, we determine that **each group needs to recruit 72 subjects**.

In summary, this study plans to enroll a total of **144 subjects** (72 in the treatment group, 72 in the control group). This sample size is sufficient to statistically and effectively test the core hypothesis of this study and is feasible within the multi-center collaborative framework. An interim analysis will assess whether the sample size needs adjustment based on actual enrollment and data variability.

**Reference:** Liu Z, Liu Y, Xu H, et al. Effect of Electroacupuncture on Urinary Leakage Among Women With Stress Urinary Incontinence: A Randomized Clinical Trial. *JAMA*. 2017;317(24):2493–2501. doi:10.1001/jama.2017.7220

**(3) Study Period** 2025.08.01——2027.08.01

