## (7) Treatment Methods

All patients will have their urinary catheter removed on postoperative day 14 (POD14). The early electroacupuncture intervention (including real electroacupuncture and sham electroacupuncture) will be initiated on postoperative day 7 (POD 7), with subsequent sessions on POD 9 and POD 11, for a total of 3 sessions.

**Treatment Group:** Receive electroacupuncture at acupoints including Shenshu (BL23), Pangguangshu (BL28), and Baliao (BL31-34), 30 minutes each time. A continuous wave of 2Hz will be used initially, with the intensity gradually increased to a level that is comfortable for the patient. The current intensity will be 1-5mA and can be gradually increased to the maximum tolerable level for the patient.

**Control Group:** Will use non-invasive sham acupuncture needles: validated blunt-tip, non-penetrating needles (such as Park or Streitberger needles). When pressure is applied, the needle tip retracts into the handle, giving the patient a sensation of pressure on the skin, but it does not puncture the skin. The procedure will be performed at **non-acupoints** (points 1-2 cm away from the real acupoints but not on the same meridian). The electroacupuncture device clips will also be attached to the sham needle handles, and the device will be turned on (emitting the same sound or light indicators), but **no electrical current will be delivered**. This ensures the entire treatment scenario is visually and auditorily identical to the real treatment group.

To ensure all subjects receive consistent standard postoperative rehabilitation guidance and to control for potential confounding variables, all successfully enrolled

patients (regardless of group) will receive standardized Pelvic Floor Muscle Training (PFMT) health education on POD 7 (the same day as the first intervention).

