## 6. Innovative Aspects of the Project

Currently, research on the impact of early acupuncture intervention on immediate urinary continence after catheter removal in post-RP patients is a blank slate. This study aims to fill this research gap by evaluating the effect of early postoperative acupuncture treatment on patients' immediate continence ability through a prospective controlled study. The specific objective is: To systematically evaluate the efficacy of early acupuncture intervention by comparing the intervention group (early acupuncture + standard care) versus the control group (sham acupuncture + standard care) in terms of urine leakage volume, proportion of complete continence, pad usage, and patient satisfaction within 24 hours after catheter removal. If the study results confirm the expectations, it will provide a new, non-invasive intervention for clinical practice, significantly improving the quality of patient's postoperative recovery and reducing the burden on the healthcare system. This study will directly address the core issue of generally low-quality evidence in this field by employing a gold-standard research design. It focuses on the POD 7-14 window, an intervention period not yet systematically studied, to explore the impact of early acupuncture intervention on immediate continence upon catheter removal. It is expected to provide high-level evidence for improving the early postoperative quality of life for prostate cancer patients. Furthermore, this study will promote the integration of traditional Chinese medicine with modern medicine, providing new therapeutic ideas and practical evidence for post-prostatectomy rehabilitation globally.

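### The primary endpoint is set at two different times, the first hour after catheter removal and the 1-week follow-up, and the outcome lists omit the promised within-24-hour assessment

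*Protocol*

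**What the plan says.** **Sample Size** (under the enrolment numbers by center) states that the primary endpoint has been determined as leakage in grams on the "1-hour pad test administered immediately after catheter removal (within the first 1 hour post-removal"). The calculation of 64 evaluable and 72 recruited per group is attached to that definition.

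**Outcome Measures, item 1**, and **Efficacy Evaluation, item 1**, also under the label of primary endpoint, both give "Urine leakage volume (grams) measured by the first 1-hour pad test during the follow-up at 1 week post-catheter removal".

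**(7) Treatment Methods** fixes the reference day: "All patients will have their urinary catheter removed on postoperative day 14 (POD14"). The Enrollment and Treatment Protocol section repeats it.

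The other statements of what the trial measures are:

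- **II.1 Study Objectives** gives no time window: "To evaluate the effect of early electroacupuncture intervention on immediate urinary continence after prostatectomy in a prospective study".
- **1. Rationale** closes with a specific objective comparing the groups "in terms of urine leakage volume, proportion of complete continence, pad usage, and patient satisfaction within 24 hours after catheter removal". **6. Innovative Aspects of the Project** repeats it: "proportion of complete continence, pad usage, and patient satisfaction within 24 hours after catheter removal".
- **Clinical Operational Feasibility** says that an assessment within 24 hours of removal, with pad test and complete continence as examples, will be completed. It then describes separately a follow-up plan that begins at 1 week.
- **Outcome Measures, item 2**, places the remaining pad tests thus: "Conducted at the 4-week and 24-week follow-ups".
- **Outcome Measures, item 3**, an ICIQ-SF questionnaire item scheduled at weeks 1, 4, 8, 12 and 24, adds: "The proportion of completely continent patients (zero leakage) will directly quantify immediate continence".

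**The concern.** A confirmatory trial needs one primary variable at one time, and this protocol names two. Leakage in the first hour after the catheter comes out and leakage a week later are different quantities. The treatment effect, the spread of the data and the amount of missing data may all differ between them, and one could be significant without the other.

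Other parts of the protocol depend on the answer. The interim review may adjust the sample size according to data variability, but it is unclear whose variability. Multiple imputation and the primary analysis have two candidate targets.

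There is also a practical risk. The outcome lists are what a site would schedule from, and they contain no removal-day measurement. A first-hour pad test that was not done cannot be recovered later. The trial could then finish without the endpoint named in its sample-size section and without the within-24-hour comparison named in its specific objective.

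**Working it through.** **1. Gap between the two primary times.** Removal is on POD 14. The first-hour test is therefore on POD 14, and the 1-week test is at 14 + 7 = about POD 21. The gap is 7 days.

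**2. Can the two definitions be read as one?** No. In the lists, the word for the first test is tied to the 1-week follow-up, not to the removal day. Clinical Operational Feasibility treats the within-24-hour assessment and the follow-up from 1 week onward as separate occasions, so week 1 is not a loose name for removal day.

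**3. What the outcome lists cover, against the specific objective.**

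| Item named for the first 24 hours | In the outcome lists? | Time given there |
|---|---|---|
| Leakage volume | Yes | Pad tests at weeks 1, 4, 24 |
| Complete continence | Yes, under the ICIQ-SF item | Item scheduled at weeks 1, 4, 8, 12, 24; no removal-day time |
| Pad usage | No | None |
| Patient satisfaction | No | None |

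Of the 3 listed pad tests, 0 fall within 24 hours of removal. Of the 4 items, 2 are absent and 2 have no removal-day time.

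**4. Sample size.** The inputs, all from the Sample Size text, are two-sided α = 0.05, power 0.80, 1:1 allocation, δ = 7.4 g, σ = 14.9 g and 10% dropout.

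- n per group = (1.960 + 0.842)² × 2 × 14.9² / 7.4² = 7.849 × 444.02 / 54.76 = 63.64, so 64.
- With dropout: 64 / 0.90 = 71.11, so 72 per group.
- Total: 2 × 72 = 144, which equals the center totals 84 + 30 + 30.

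The plan's figures reproduce. Power is 80.2% at 64 per group and 84.6% at 72. The formula contains no time of assessment, so the same inputs give the same size for either time. The inputs themselves are a difference in reduction and an SD of change from an external trial in women, and the protocol ties them to neither time.

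**5. Illustration of what an open choice could cost.** If the time were chosen after seeing both results, each tested at 0.05, the chance of at least one false positive would be 5% if the two results were perfectly correlated. It would be 1 − 0.95² = 9.75% if they were independent. The actual correlation is unknown, so this range is an assumption and not an estimate for this trial.

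**The case against.** The best reply is that either time is a legitimate choice, that two lists agree on week 1 against one paragraph, and that the within-24-hour wording sits in rationale and feasibility narrative. But the two lists are the same text printed twice, and the Sample Size paragraph is an operative definition too. The conflict needs only those three places. A statistical analysis plan might choose between them, but the protocol would still name two primaries.

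Several narrower objections do stand:

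- That the sample size is unchanged holds only on the stated inputs. Whether 7.4 g and 14.9 g suit the chosen time is not shown. Purely as an assumption, with δ kept at 7.4 g, an SD of 20 g would need 115 per group, and 64 per group would then have 55% power.
- Only the Sample Size text specifies a 1-hour test in the first hour. The 24-hour statements are compatible with a removal-day test but do not name it, and the formal objective gives no window.
- The sentence on complete continence carries no time of its own. Its position under a questionnaire item that starts at week 1 suggests the timing but does not state it.
- The gap on pad usage and satisfaction is real, but it would not by itself be as serious as the two primary times.

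**Conclusion.** The concern holds and must be fixed. Current text defines the primary endpoint at two times 7 days apart, with no statement of which governs. The outcome lists contain no measurement within 24 hours of removal, although the specific objective and the feasibility section promise one. Two of the four items in that objective, pad usage and satisfaction, are not listed as outcomes at all.

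The conclusion rests on reading the passages against each other and needs no numerical assumption. A week-1 result would still inform early continence, but it is neither the first-hour endpoint nor the within-24-hour comparison. No arithmetic error is claimed: 64, 72 and 144 follow from the stated inputs.

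**What to change.** Before any outcome data are examined:

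1. Name one primary time and state it identically in Sample Size, Outcome Measures and Efficacy Evaluation. List the other pad test as secondary if it is collected.
2. If the removal-day test is chosen, add it to both outcome lists and to the schedule. If week 1 is chosen, align the wording on immediate and within-24-hour continence in Rationale, Study Objectives, Clinical Operational Feasibility, Innovative Aspects and Expected Research Outcomes.
3. Either remove pad usage and satisfaction from the specific objective (Rationale and Innovative Aspects) and from Expected Research Outcomes, or list them as outcomes with an instrument and a time. Give complete continence an explicit time.
4. State which time the 7.4 g and 14.9 g inputs are meant to describe.
5. As a clarification only, say that pad tests are done at an in-person visit, since the feasibility section allows follow-up by telephone or outpatient visit.

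The cost is protocol wording and at most one removal-day pad test, which the Sample Size text already defines and the feasibility section's within-24-hour assessment could accommodate. Keeping pad usage and satisfaction would add some data collection, including a satisfaction instrument, as none is named. The sample size stays at 144 provided the stated inputs are kept for the chosen time.
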